## 1. INTRODUCTION

This statistical analysis plan (SAP) is designed in compliance with ICH E9 to outline the methods to be used in the analysis of study data in order to evaluate the study objective(s) from Arrowhead Pharmaceuticals, Inc. (Sponsor) protocol AROENaC1001 Version 4.0, dated 09 April 2021. Populations for analysis, data handling rules, statistical methods, and formats for data presentation are provided. The statistical analyses and summary tabulations described in this SAP will provide the basis for the results sections of the clinical study report (CSR) for this trial.

An approved and signed SAP is required prior to database lock and prior to the planned unblinding and analysis of an ongoing cohort. Completed cohorts may be unblinded without a signed SAP.

The formats for the tables, figures, listings (TFLs) described in this SAP are provided in a companion document. A table of contents for the TFLs will be included.

EMB Statistical Solutions, LLC (EMB) will have responsibility for performing the analyses outlined in this SAP. The Sponsor will have responsibility for performing the PK noncompartmental analysis (NCA) (Appendix B).

## 2. OBJECTIVES, ENDPOINTS AND HYPOTHESES

### 2.1 Objectives and Endpoints/Estimands

The objective of the study is to assess the safety, tolerability, pharmacokinetics (PK) of ARO-ENaC in normal healthy volunteers (NHVs) and patients with Cystic Fibrosis (CF).

Endpoints
Primary

The incidence and frequency of adverse events (AEs) over time through end of study using escalating multiple doses in NHVs and in CF patients.

Secondary

Changes from pre-dose baseline in serum electrolytes in NHVs and CF patients as a safety measure.

Changes from pre-dose baseline in Forced Expiratory Volume (FEV1) in NHVs as a measure of safety.

Pharmacokinetics of ARO-ENaC in NHVs and in CF patients.

Exploratory

Changes from pre-dose baseline in FEV1 in CF patients

Changes from pre-dose baseline in lung clearance index (LCI) in CF patients

Changes from pre-dose baseline in the revised cystic fibrosis questionnaire (CFQ-R) in CF patients

Rate of pulmonary exacerbations in CF patients receiving ARO-ENaC versus placebo (PBO)

Changes from pre-dose baseline in body mass index (BMI) in CF patients

- Plasma metabolite identification in NHVs (reported in a separate report outside of this study)
- Determination of urinary excretion and metabolite identification in NHVs (reported in a separate report outside of this study)
- Changes from pre-dose baseline to Day 18 in expression of  $\alpha$ ENaC using bronchoscopic brush biopsy samples in NHVs
- Changes from pre-dose baseline to Day 18 in expression of  $\alpha$ ENaC using bronchoalveolar lavage (BAL) samples in NHVs
- Changes from pre-dose baseline to Day 18 in cytokine levels as well as cell count and differential in BAL fluid in NHVs

## 2.2 Hypotheses and/or Estimations

No formal hypothesis testing will be performed.

## 3. STUDY OVERVIEW

### 3.1 Study Design

This is a phase 1/2a first-in-human dose-ranging study to assess the safety, tolerability and PK of ARO-ENaC in NHV and in patients with CF.

#### Normal Healthy Volunteers:

For NHVs, 4 cohorts of 6 eligible subjects (4 active: 2 placebo) will be evaluated at each dose level starting with Cohort 1. Cohort 5 will include 12 eligible patients (8 active: 4 placebo) who will be treated with a dose equal to or less than that given to Cohort 4, with the purpose of collecting bronchoscopic samples to evaluate for  $\alpha$ ENaC mRNA knockdown. NHV cohorts will receive a single cycle of three doses all at a fixed dose level administered daily on Days 1, 2, 3.

NHV cohorts 1-4 will begin with administration of ARO-ENaC or PBO to two sentinel participants (one ARO-ENaC, one PBO). Following the Day 4 evaluation in these participants, if there are no significant safety concerns based on PI's judgement, the remaining participants in the cohort will be dosed. Cohort 5 will not utilize sentinel participants as the dose evaluated in Cohort 5 will be equal to or lower than doses used in Cohorts 1-4. Dosing of participants will be staggered by at least 30 minutes such that no two participants will be dosed simultaneously. Blood samples will be drawn pre-dose on Day 1 for baseline measurements.

Based on observations for all NHV subjects through Day 21, and experience from any prior cohorts, the Data Safety Committee (DSC) will meet to vote on dose escalation to next NHV cohort and initiation of CF cohorts, when applicable.

Following an affirmative vote from the DSC meeting held during NHV Cohort 4 allowing the opening of CF Cohort 4b, NHV Cohort 5 may also be subsequently opened for accrual. The primary purpose of Cohort 5 will be to assess the effect of ARO-ENaC on  $\alpha$ ENaC mRNA expression, with samples obtained via bronchoscopy. The dose in Cohort 5 will be equivalent to

or less than the dose utilized in Cohort 4. Based on available safety data reviewed during prior DSC meetings, the Sponsor or DSC may adjust the dose in Cohort 5 downward.

Cystic Fibrosis Patients:

Cohorts 2b, 3b, 4b will enroll eligible CF patients to receive two cycles of ARO-ENaC or PBO administered daily on Days 1, 2 and 3, then again on Days 22, 23 and 24. CF patient cohorts 2b, 3b, and 4b will be opened for accrual once the corresponding NHV cohort receiving the same dose level has reached Day 21 and based on DSC vote that it is safe to proceed. CF patient cohorts 2b, 3b, and 4b will enroll in sequence with 2b enrolling first, followed by 3b and then Cohort 4b. Each cohort 2b and 3b will enroll 4 subjects to receive active drug and 2 subjects to receive placebo. Cohort 4b will enroll 9 subjects to receive active drug and 3 subjects to receive placebo.

Once all subjects in CF Cohort 4b have completed the Day 29 study visit, the DSC will meet to review all cumulative safety data to date and to vote on the initiation of CF Cohort 6. The purpose of Cohort 6 is to assess the safety and efficacy of an alternate dosing regimen. In CF Cohort 6, the 3-day dosing cycle used in Cohort 4b is compressed to a single dose, which is given at 2 week intervals, such that subjects will be dosed on Days 1, 15, and 29. The dose given on each dosing day to a subject in CF Cohort 6 (in respirable delivered dose [RDD] terms, which represents the amount of drug that reaches the lung, as opposed to the amount of drug loaded into the nebulizer) will be  $\leq$  3x the dose given on each dosing day to a subject in CF Cohort 4b. Thus, the dose (in RDD terms) given on Day 1 to a subject in Cohort 6 will be  $\leq$  the total cumulative dosage given over Days 1, 2, and 3 to a subject in Cohort 4b. Of note, the RDD does not scale identically to the nebulizer loaded dose (i.e. tripling the RDD does not necessarily result in tripling the nebulizer loaded dose). Cohort 6 will enroll 18 subjects to receive active drug and 6 subjects to receive placebo.

Table 4 from Protocol: Cohort Summary

Cohort	Population	Blinding	# Subjects	Dosing Schedule
1	NHVs	Double-blind	6 (4 active: 2 PBO)	20 mg Day 1, 2, 3
2	NHVs	Double-blind	6 (4 active: 2 PBO)	40 mg Day 1, 2, 3
3	NHVs	Double-blind	6 (4 active: 2 PBO)	65 mg Day 1, 2, 3
4	NHVs	Double-blind	6 (4 active: 2 PBO)	<math>\leq</math> 180 mg Day 1, 2, 3
5	NHVs	Double-blind	12 (8 active: 4 PBO)	<math>\leq</math> 180 mg Day 1, 2, 3
2b	CF Patients	Double-blind	Up to 6 (4 active: 2 PBO)	<math>\leq</math> 40 mg Day 1, 2, 3; <math>\leq</math> 40 mg Day 22, 23, 24
3b	CF Patients	Double-blind	Up to 6 (4 active: 2 PBO)	<math>\leq</math> 65 mg Day 1, 2, 3; <math>\leq</math> 65 mg Day 22, 23, 24
4b	CF Patients (ppFEV <math>></math> 70%)	Double-blind	Up to 12 (9 active: 3 PBO)	<math>\leq</math> 180 mg Day 1, 2, 3; <math>\leq</math> 180 mg Day 22, 23, 24
6	CF Patients	Double-blind	Up to 24 (18 active: 6 PBO)	<math>\leq</math> 490 mg Day 1; <math>\leq</math> 490 mg Day 15; <math>\leq</math> 490 mg Day 29

Principal investigators (PIs) and study participants will remain blinded through End-of-Study (EOS). EMB may be unblinded prior to the completion of a cohort to provide unblinded interim analyses to a designated unblinded team at the Sponsor (outlined in the Matrix of Access to Restricted Data). With the exception of Cohort 6, the Sponsor (apart from the designated unblinded

team) will remain blinded until all subjects in a cohort have completed the EOS visit (or discontinued early) at which time they may be unblinded to that cohort. For Cohort 6, the Sponsor may be unblinded prior to completion of the cohort. Apart from the unblinding detailed above, blinding (where applicable) will be preserved to the extent possible. However, treatment unblinding of an individual participant may occur, at the discretion of the PI or Medical Monitor, where deemed necessary for treatment of an AE or for a decision to be made regarding trial continuation.

[figure not shown]
### 3.2 Sample Size

Sample sizes for NHV Cohorts 1-5 and CF cohorts 2b, 3b, and 4b are decided based on the probability of observing at least one TEAE from each cohort. When probability of observing TEAE from a single subject who received active drug is 30%, chance of observing at least one TEAE will be higher than 75%, among 4 dosed subjects. With cohort size 8 or 9 (Cohorts 4b and 5), probability of seeing at least one TEAE would be approximately 85% and 95% if assumed probabilities of observing AE from a single dosed subject are 20% and 30%, respectively. The table below lists probabilities of observing at least one TEAE under various scenarios.

Table 5 from Protocol: Sample Size Calculation for Cohorts 1-5 and 2b, 3b and 4b

Probability of observing at least one TEAE from each dosed subject	Number of subjects treated per Cohort	Probability of observing at least one TEAE from Cohort
0.2	4	0.59
0.3	4	0.76
0.2	5	0.67
0.3	5	0.83
0.2	6	0.74
0.3	6	0.88
0.2	7	0.79
0.3	7	0.92
0.2	8	0.83
0.3	8	0.94
0.2	9	0.87
0.3	9	0.96
0.2	10	0.89
0.3	10	0.97

Figure 2 from Protocol: Relationship between Sample Size for a Cohort and Probability of Observing at Least One TEAE within a Cohort

Sample size for Cohort 6 is calculated to have more than 80% power to observe 5% absolute change from baseline in ppFEV1 at Day 43 at significance level 0.05, with standard deviation 7%.

No stratification is planned in this study.

## 4. COVARIATES AND SUBGROUPS

### 4.1 Planned Covariates

There are no predetermined covariates.

### 4.2 Subgroups

Subgroup analyses of Spirometry and LCI for CF patient cohorts will be categorized as follow.

- CFTR mutation status
- Use of CFTR modulators at baseline (Y/N)
- Use of inhaled hypertonic saline at baseline (Y/N)

## 5. DEFINITIONS

### Study Day:

Day of study relative to the date of first dose of active drug or placebo. First dose date will be considered as Day 1. Calculated prior to first dose date as (date of measurement – date of first dose) and calculated after first dose date as (date of measurement – date of first dose + 1).

Baseline:

The last observation prior to the first dose of active drug or placebo. The baseline value may be an unscheduled or repeated measurement.

Change (absolute) from baseline:

The arithmetic difference between a post-baseline value and baseline for a given time point: change (absolute) from baseline = (post-dose value – baseline value).

Percent change from baseline:

The percent change between a post-baseline value and baseline for a given time point: [(post-dose value – baseline value) / baseline value] \*100%

Treatment-emergent AEs (TEAEs):

TEAE will be derived as any AEs occurring on or after the first dose.

Treatment-emergent SAEs (TESAEs):

TESAE will be derived as any serious AEs occurring on or after the first dose.

Concomitant Medications:

Concomitant medications will be derived as any medications with an end date on or after the first dose.

Use of medications at baseline:

For each of the following medications: CFTR modulators, inhaled hypertonic saline, inhaled bronchodilators, chronic inhaled antibiotics, inhaled corticosteroids, dornase alfa, and azithromycin, any use within 30 days prior to first dose will be considered as use at baseline. Dornase alfa and azithromycin will be identified by the Preferred Drug Name as coded by WHODrug. All other medications will be identified as recorded on the CF-Concomitant Medications eCRF.

Sputum pseudomonas status at baseline:

Any pseudomonas (as collected on the Airway Infection eCRF) present within 30 days prior to first dose will be considered as positive at baseline.

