6.1. Primary Endpoint

1. The incidence and frequency of adverse events over time through end of study using escalating multiple doses in NHVs and in CF patients.

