10.7. Safety Assessments

The safety of ARO-ENaC will be evaluated by collection of the following measurements performed at time points as specified in the SOA as well as CS changes from baseline to scheduled time points:

- Monitoring of AEs/SAEs
- Physical examinations
- Vital signs
- ECG measurements
- Chest X-rays
- Measurement of serum and urine electrolytes

- Spirometry
- Clinical laboratory tests (hematology, chemistry, coagulation, urinalysis)
- Concomitant medications/therapy
- Reasons for treatment discontinuation due to toxicity

The AE/SAE reporting period for an enrolled participant will begin when the participant provides informed consent. Treatment-Emergent AEs/SAEs will be those defined as following dose administration. All AEs/SAEs that occur during the AE reporting period specified in the protocol must be reported to Arrowhead Pharmaceuticals, Inc. regardless of the relationship of the AE to study treatment. Any known untoward event that occurs beyond the AE reporting period that the PI considers an SAE and possibly related to study treatment will be reported to Arrowhead.

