11. ADVERSE EVENTS

The PI and clinical facility staff are responsible for detection, recording and reporting of events that meet the criteria and definition of various AEs as listed below. Adverse events will be recorded from time of signed consent through to EOS; only AEs that occur post-dose will be considered treatment-emergent. The PI and clinical facility staff are responsible for detection, recording and reporting of pregnancy and appropriate follow up. Any known pregnancy that occurs within 90 days following the end of study visit should be reported by the subject to the PI. Information regarding any reported pregnancy should be collected for at least 1 year after birth or longer if it is decided that additional follow-up is required or until the end of the pregnancy.

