11.1. Definitions

An **Adverse Event (AE)** is any untoward medical occurrence in a patient or clinical investigation patient administered a pharmaceutical product and which does not necessarily have to have a causal relationship with this treatment. An AE can therefore be any unfavorable and unintended sign (including an abnormal laboratory finding or diagnostic test), symptom, or disease temporally associated with the use of a medicinal (investigational/experimental) product, whether related to this product or not. (Refer to ICH E2a: Clinical Safety Data Management: Definitions and Standards for Expedited Reporting, 27 October 1994).

Treatment-emergent AEs will be defined as AEs with onset after administration of the study drug, or when a pre-existing medical condition increases in severity or frequency after study drug administration.

AEs will not include:

- A medical procedure such as surgery, endoscopy, tooth extraction, or transfusion (although the condition that leads to the procedure may be an AE)
- A pre-existing disease or condition present at the start of the study that does not worsen during the study
- Any situation where an untoward medical occurrence has not occurred (for example, hospitalizations for cosmetic elective surgery or “social” admissions)
- An overdose of either the investigational product or a concurrent medication without any resulting signs or symptoms

A **Serious Adverse Event (SAE)** is an AE that:

- Results in death

- Is life-threatening (NOTE: The term ‘life-threatening’ in the definition of ‘serious’ refers to an event/reaction in which the participant was at immediate risk of death at the time of the event/reaction; it does not refer to an event/reaction which hypothetically might have caused death, if it were more severe)
- Requires inpatient hospitalization or prolongation of an existing hospitalization
- Results in persistent or significant disability/incapacity
- Is a congenital anomaly/birth defect
- Is a medically important event or reaction

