### 10. CHANGES FROM PROTOCOL-SPECIFIED ANALYSES

There are no major changes between the protocol-defined statistical analyses and those presented in this statistical plan.

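### SAP Section 5 omits the protocol's worsening clause from the TEAE and TESAE definitions, so a screening-period AE that worsens after dosing can drop out of the TEAE tables

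*SAP*

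**What the plan says.** Protocol Section 11.1 gives two routes to treatment-emergent status. The first is new onset: "Treatment-emergent AEs will be defined as AEs with onset after administration of the study drug". The second is worsening: "or when a pre-existing medical condition increases in severity or frequency after study drug administration". The same section removes from the AE definition only "A pre-existing disease or condition present at the start of the study that does not worsen during the study", so a condition that does worsen can be an AE.

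Elsewhere the protocol uses a shorter rule with no worsening clause. Section 10.7 says: "Treatment-Emergent AEs/SAEs will be those defined as following dose administration". Section 11 says "only AEs that occur post-dose will be considered treatment-emergent", and Section 11.3 repeats this.

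SAP Section 5 says: "TEAE will be derived as any AEs occurring on or after the first dose". Its TESAE definition has the same form. SAP Section 8.2 imputes missing start dates to settle treatment-emergent status, so the derivation runs on onset. SAP Section 10 says: "There are no major changes between the protocol-defined statistical analyses and those presented in this statistical plan".

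The primary endpoint (Protocol Section 6.1, repeated in SAP Section 2.1) is worded on AEs: "The incidence and frequency of adverse events over time through end of study". SAP Section 9.5.1 divides the reporting as follows:

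- The overall summary counts all AEs and all SAEs, next to TEAEs and TESAEs.
- The main tables by system organ class (SOC) and preferred term (PT) cover TEAEs, TESAEs and their treatment-related subsets.
- The severity and relationship tables cover TEAEs only.
- Tables of AEs leading to drug withdrawal or study discontinuation are not limited to TEAEs.
- Every AE is listed.

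**The concern.** AEs are collected from consent, and screening can run for 28 days before Day 1, so an AE can have a start date before the first inhalation. Suppose a mild cough begins in screening and becomes severe after dosing. If it stays one record with its original start date, Protocol Section 11.1 makes it treatment-emergent and SAP Section 5 does not.

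The tables that would lose it are those a reader uses to judge which events occurred, how severe they were and whether they were thought related. The all-AE row is a weak substitute: it mixes pre-dose and post-dose events and shows no SOC, PT or severity. Protocol Section 5.6 notes that pulmonary status may fluctuate in CF patients, so post-dose worsening of a respiratory event is plausible in a trial of an inhaled drug. With few active subjects per cohort, one reclassified subject is visible in a percentage.

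**Working it through.** **Step 1. Compare the rules.** Four cases cover the possibilities.

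| Case | Protocol 11.1 | SAP 5 |
|---|---|---|
| A. New event, starts after dosing | TEAE | TEAE |
| B. Medical-history condition worsens after dosing, entered as a new AE with a post-dose start | TEAE | TEAE |
| C. AE starts between consent and first dose, worsens after dosing, worsening entered as a second record with its own start date | TEAE | TEAE |
| D. As C, but kept as one record with the original start date | TEAE | Not a TEAE |

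Only case D separates the two definitions. It reads pre-existing as present before the first dose, since the clause measures change from study drug administration.

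**Step 2. Is case D ruled out?** No. Protocol Section 11.5.1 assigns each AE one severity category. Section 11.6 has the existing AE page updated once the event resolves. Neither document requires a worsening to be entered as a new record with its own start date. Neither says the opposite, so how often case D arises is unknown.

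**Step 3. Where does a case D event go?** By SAP Section 9.5.1 it leaves the TEAE tables by SOC and PT, by severity and by relationship, and the TESAE tables if it is serious. It stays in the all-AE (and all-SAE) rows, the listings and, if it led to withdrawal or discontinuation, the tables for those outcomes.

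**Step 4. The plan's own TEAE figure.** Table 5 (Protocol Section 12.1, SAP Section 3.2) is the only figure built on TEAEs. The formula is 1 − (1 − p)^n. For p = 0.3 and n = 4: 1 − 0.7^4 = 1 − 0.2401 = 0.7599, against 0.76 stated. For p = 0.2 and n = 9: 1 − 0.8^9 = 0.8658, against 0.87 stated. All 14 rows reproduce to two decimals. No stated figure changes with the choice of definition.

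**Step 5. Size of one omitted subject.** The planned active numbers in the CF cohorts are 4 (2b and 3b), 9 (4b) and 18 (6):

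- 1/4 = 25 percentage points
- 1/9 = 11 percentage points
- 1/18 = 5.6 percentage points

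These apply to a table row only if the subject has no other TEAE in that row, and to overall TEAE incidence only if the subject has no other TEAE at all.

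**Step 6. Illustration under an assumption.** The documents do not say what share of TEAEs would be case D. Let w be an assumed share of the per-subject TEAE probability that is lost, so that p becomes p(1 − w).

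| w | n = 4, p = 0.3 | n = 9, p = 0.3 |
|---|---|---|
| 0 | 0.76 | 0.96 |
| 5% | 0.74 | 0.95 |
| 10% | 0.72 | 0.94 |
| 20% | 0.67 | 0.92 |

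For example, with w = 10% and n = 4: 1 − (1 − 0.27)^4 = 0.716. The values of w are not estimates.

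**The case against.** The strongest reply is that the SAP agrees with three places in the protocol (Sections 10.7, 11 and 11.3) and departs from one, and that the gap is narrow. This stands in part. The short statements can be read consistently with Section 11.1, since a post-dose worsening does occur after dosing. If they are read as conflicting, the protocol needs reconciling as well as the SAP. Either way, Section 11.1 is the formal definition, and nothing in the SAP restores its second route.

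A reader might also infer more than the documents support:

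- *That the event is lost from the primary endpoint.* The endpoint is worded on AEs, and the event stays in the all-AE row and the listings. The loss is from the TEAE tables.
- *That long-standing CF cough, sputum or dyspnea that worsens would be missed.* Conditions present before consent are medical history (Protocol Section 11.3). If worsening is entered as a new AE with a post-dose start, SAP Section 5 captures it. The exposed group is AEs that arise between consent and first dose. Eligibility narrows it, because a CF exacerbation within 30 days of first dose is excluded. Spirometry and exacerbations are also summarized separately.
- *That the SAP rule is biased toward fewer events.* The missing clause removes events, but SAP Section 8.2 sets some missing or partial start dates to Study Day 1 or the first dose, which adds them. The net direction is not determinable. The same rule applies to active and placebo subjects.
- *That Day 1 events before inhalation are certainly counted.* SAP Section 5 refers to the first dose, not its date. The SAP does not say whether onset time is used, so this is a possibility only.
- *That SAP Section 10 claims nothing changed.* It denies major changes only.

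**Conclusion.** The discrepancy is real and rests on a stated rule, not on a missing detail. SAP Section 5 omits the worsening route in Protocol Section 11.1 for both TEAEs and TESAEs, and SAP Section 10 does not disclose it. The consequence is confined to AEs that start between consent and first dose, worsen after dosing and are kept as single records. They drop out of the TEAE tables that report most of the primary safety analysis.

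The conclusion rests on two assumptions: that pre-existing in Section 11.1 means present before dosing, and that the case report form does not force a new record at worsening. The documents settle neither. The per-subject effect is in Step 5, with its condition. How many subjects are affected is unknown. The point should be fixed before unblinding, but it does not threaten the primary endpoint as worded.

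**What to change.** 1. In SAP Section 5, add the worsening route of Protocol Section 11.1 to the TEAE and TESAE definitions. Alternatively, state there and in the recording instructions that any rise in an event's severity or frequency after dosing is entered as a new AE with its own start date.
2. Reconcile Protocol Sections 10.7, 11 and 11.3 with Section 11.1, so that one definition governs.
3. For Day 1 events, classify by onset time relative to the first inhalation where a time is recorded, and say what is done where it is not.
4. Record the resolution in SAP Section 10.

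The cost is a few sentences and minor programming. TEAE counts may rise slightly.

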8.2. Inclusion Criteria

Applicable to NHV and CF Cohorts

To be eligible for participation, NHVs and CF patients must meet all the following inclusion criteria:

1. Male or non-pregnant, non-lactating female volunteers 18-55 years of age, inclusive at time of Screening
2. Normal ppFEV1 (>80%) at Screening in NHVs only
3. Able and willing to provide written informed consent prior to the performance of any study specific procedures
4. Participants with a BMI between 18.0 and 35.0 kg/m², inclusive, at Screening
5. A 12-lead ECG at Screening with no abnormalities that may compromise participant's safety in this study
6. Non-smoker (smoker is defined as smoking cigarettes daily for at least the past 12 months) with current non-smoking status confirmed by urine cotinine at Screening AND any previous smoking history prior to 12 months must be < 15 pack years. Patients may be on nicotine replacement (patch or gum). e-cigarettes (vapor) is not permitted. A positive urine cotinine result due to nicotine replacement is acceptable for enrollment at the discretion of the PI.
7. Participants of childbearing potential must agree to use highly-effective contraception during the study and for at least 12 weeks following the end of the study or last dose of study drug, whichever is later. Males must not donate sperm during the study and for at least 12 weeks following the end of the study or last dose of study drug, whichever is later. (See Section 10.6 for details regarding highly-effective contraception).
8. Participants who are willing and able to comply with all study assessments and adhere to the protocol schedule
9. No abnormal finding of clinical relevance at the Screening evaluation other than CF for CF patients
10. No planned significant dietary changes during the study period.

Additional Inclusion Criteria for CF Patients

To be eligible for participation, CF patients must meet all the following inclusion criteria:

1. All other treatments for CF (including CFTR modulators/correctors) have been stable for at least two months (meaning no new medications or changes in dose) prior to first dose and patient is willing to continue this treatment regimen without change for study duration.
2. Confirmed diagnosis of CF based on source verifiable medical record
3. Percent predicted FEV1 of ≥ 40 to $\leq 90\%$ adjusted for age, sex, and height according to NHANES III at the Screening Visit. For Cohort 4b patients must have ppFEV1 $> 70\%$.

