### 8.2 Handling of Missing and Incomplete Data

Missing values will not be imputed, except in the case of determining treatment-emergent status for AEs, concomitant status for medication and procedures, and for missing or partial dates where a complete date is required for calculations.

Missing	Imputation	Exception
Day	01	Default to Study Day 1 if an AE, medication/procedure starts the same year and month as Study Day 1 and the end date has same year and month as Study Day 1 or later.
Day / Month	01 / Jan	Default to Study Day 1 if an AE, medication/procedure starts the same year as Study Day 1 and the end date has same year as Study Day 1 or later.
Day / Month / Year	To calculate a missing start date: 

If a partial or complete stop date is present:

Stop date < first dosing date: impute January 1 of the stop year

Stop date <math>\geq</math> first dosing date: impute the date of first dose

If it is unknown whether the stop date is < or <math>\geq</math> first dosing date due to a missing or partial stop date, or if a stop date is not

	

	collected: impute date of first dose.	
--	---------------------------------------	--

Medications and procedures with missing or partial end dates will be assumed to be concomitant unless a partial end date documents it as ending prior to treatment.

The original missing or partial date, the imputed complete date, and an indicator variable that indicates which dates were imputed will be retained in the database. Dates will be presented as collected in all listings. Imputed dates will not be presented in listings but may be used for summary tables.

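### Read literally, the SAP's start-date imputation labels a long-standing CFTR modulator or hypertonic saline user with no recorded start date as a non-user at baseline

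*SAP*

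**What the plan says.** **Definition.** SAP section 5 applies one timing rule to seven CF background medications: "any use within 30 days prior to first dose will be considered as use at baseline". Dornase alfa and azithromycin are found by coded drug name. For the other five, including CFTR modulators and inhaled hypertonic saline, "All other medications will be identified as recorded on the CF-Concomitant Medications eCRF".

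**Imputation.** SAP 8.2 rules out imputing missing values except for three purposes: treatment-emergent status of AEs, "concomitant status for medication and procedures", and "for missing or partial dates where a complete date is required for calculations". For a fully missing start date whose stop date is on or after dosing, the instruction is "first dosing date: impute the date of first dose". Where the stop date cannot be placed relative to dosing, or was not gathered, the instruction ends "collected: impute date of first dose". If the stop date precedes dosing, the start becomes 1 January of the stop year. A start known only to the year, or to the month, goes to the first of that year or month. The exception is a start in the same year or month as Study Day 1 with an end date in that period or later, which goes to Study Day 1.

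**Eligibility.** Protocol 8.2, CF inclusion criterion 1, requires that before first dose "All other treatments for CF (including CFTR modulators/correctors) have been stable for at least two months".

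**Where the flag is used.** SAP 4.2 makes modulator use and hypertonic saline use two of the three subgroup factors for spirometry and LCI. SAP 9.4.1 lists all seven flags in the CF baseline table.

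**The concern.** Moving an unknown start towards first dose is cautious for adverse events, because it errs towards calling them treatment-emergent. For background therapy the same rule works the other way. A drug taken for years whose start nobody can date is treated as begun on the day of dosing, so it has no use in the preceding 30 days.

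For long-standing therapy the error runs one way, from user to non-user. It would put treated patients into the untreated subgroup and blur the comparison by modulator use. That comparison matters here because protocol 5.2.3 argues that ENaC inhibition may act synergistically with CFTR modulators.

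**Working it through.** The plan states no figure to reproduce, so the check is to apply the two rules to typical records.

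**Step 1: apply SAP 8.2, then SAP 5.** The documents give no dosing date, so I assume a first dose on 15 October 2021. The 30-day window is then 15 September to 14 October if the dosing date is excluded (strict), or 15 September to 15 October if it is counted (inclusive).

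| Recorded start | Recorded stop | Start after 8.2 | Flag, strict | Flag, inclusive |
|---|---|---|---|---|
| 10 May 2019 | ongoing | 10 May 2019 | Y | Y |
| 2019 only | ongoing | 1 Jan 2019 | Y | Y |
| June 2021, no day | ongoing | 1 June 2021 | Y | Y |
| fully missing | 1 Oct 2021 | 1 Jan 2021 | Y | Y |
| fully missing | ongoing, unknown or not collected | 15 Oct 2021 | **N** | Y |
| fully missing | 1 Dec 2021 | 15 Oct 2021 | **N** | Y |
| 2021 only | 1 Dec 2021 | 15 Oct 2021 | **N** | Y |
| 2021 only | none recorded | 1 Jan 2021 | Y | Y |
| Oct 2021, no day | 1 Dec 2021 | 15 Oct 2021 | N | Y |

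The year-only row with no end date takes the Study Day 1 exception literally: the exception needs an end date, so the default of 1 January applies. If the programmer treats ongoing as a later end date, that row also becomes N on the strict reading. The last row is not long-standing therapy, since a start in the dosing month would itself breach the two-month criterion. The problem cases are therefore the three in bold.

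**Step 2: does 8.2 reach this flag?** Baseline use is not named among the purposes of imputation. However, SAP 5 and SAP 9.5.9 decide prior or concomitant status for medications from the end date alone, and 8.2 has its own rule for missing end dates. The baseline-use flag is the only medication derivation in the SAP where an imputed start would matter, and the clause on dates needed for calculations covers it.

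**Step 3: is the dosing date inside the window?** SAP 5 does not say. SAP 9.5.9 separates medications ending prior to first dose from those ending on or after it, so elsewhere the SAP's word prior excludes the dosing date. The inclusive reading would also count a drug truly begun on Day 1 as baseline use. The strict reading is the natural one.

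**Step 4: compare with eligibility.** A CF therapy in use at first dose should have been unchanged for at least two months. An imputed start on the day of dosing contradicts that. The protocol synopsis (Data Analysis) also describes the modulator subgroup in terms of a stable regimen over the last two months, so these are the patients the Y group is meant to hold.

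**Step 5: size.** The number of patients moved is U × p, where U is the number of true users and p the share with a triggering date pattern. The documents give neither, so it cannot be computed. What can be shown is the weight of one misplaced patient, since SAP 9 tabulates by dose and regimen with placebo pooled. At planned sizes one patient is 1/4 = 25% of the active arm in Cohort 2b or 3b, 1/9 = 11% in Cohort 4b, 1/18 = 6% in Cohort 6, and 1/13 = 8% of pooled CF placebo (2 + 2 + 3 + 6 = 13).

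**The case against.** The strongest reply is that the triggering record should be rare and may be settled without dates. Protocol 10.3.1 takes a medication history over the previous 30 days, the same length as the baseline window. Protocol 8.5 and 10.3.10 ask for dates of administration, and sites must judge two months' stability to enrol a patient. Protocol 14.1 provides source verification and data queries. The CF-Concomitant Medications eCRF is not shown and may carry a baseline or ongoing field. Listings show dates as collected and outputs are independently reviewed (SAP 8.2, 8.5), so a known long-term user coded N could be noticed. All of this stands, and it limits how often the problem can arise. It does not supply the missing rule, because SAP 5 cites the eCRF for identifying the drug and leaves timing to the 30-day definition.

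Two stronger readings are tempting. A reader might infer that any incomplete start date turns a user into a non-user. The table shows otherwise: an earlier known year or month, or a stop before dosing, still gives Y. A reader might also infer that the non-user subgroup is heavily contaminated. One can assume 19 users among the 24 patients of Cohort 6, with 5% to 20% of them lacking a start date. The share of true users in the N group, U × p / (non-users + U × p), then runs from 0.95/5.95 = 16% to 3.8/8.8 = 43%. With 12 users it runs from 0.6/12.6 = 5% to 2.4/14.4 = 17%. Every input is invented. The documents do not say that non-users are the smaller group or that start dates are often missing, so these figures illustrate sensitivity only.

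It is also fair to object that coding every such record Y would create the opposite error. Antibiotics can be newly started on study, since protocol 16.1 defines an exacerbation by new or changed antibiotic therapy. That objection is accepted and shapes the fix.

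**Conclusion.** The point holds on a literal reading. SAP 8.2 and SAP 5 together derive a long-standing modulator or hypertonic saline user as N in two situations: a fully missing start with a stop on or after first dose, unknown or not collected; and a year-only start in the dosing year with a recorded later end date. The conclusion assumes that imputed dates feed the flag, that the dosing date lies outside the 30-day window, and that no unseen eCRF field overrides the dates. The SAP's wording favours the first two, and the third cannot be checked from the documents.

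The consequence is modest. FEV1 and LCI in CF patients are exploratory, SAP 2.2 plans no formal hypothesis testing, and the subgroup outputs are descriptive. It is still worth correcting, because a stated rule gives a wrong subgroup label in small groups.

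**What to change.** Amend SAP 5 and 8.2 as follows.

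- State that first-dose (Study Day 1) imputation of a start date is not used for the baseline-use flag.
- For CFTR modulators, inhaled hypertonic saline and other maintenance CF therapies, count a record with a missing or partial start that is ongoing, or stopped on or after first dose, as Y. The exception is where the recorded part of the date, or other eCRF data, show a start on or after first dose.
- For inhaled antibiotics and azithromycin, set Y only if the medical history or eCRF shows use before first dose.
- Leave the imputation for treatment-emergent status of AEs unchanged.

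The cost is a few sentences in the SAP and a short change to the derivation code, with no new data collection. SAP section 1 requires a signed SAP before database lock and before planned unblinding of an ongoing cohort, so the change should be made before then.
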